7.4. Trial Duration

The trial duration from first patient enrolled to the last patient's last visit is estimated to be approximately 58 months. Patients who complete the MP are anticipated to receive 52 weeks of treatment (10 week IP + 42 week MP).

8. SELECTION AND WITHDRAWAL OF PATIENTS

8.1. Patient Inclusion Criteria

For inclusion in the trial, all of the following inclusion criteria must be fulfilled:

1. Must meet one of the following criteria:
 - Male or female adult patients aged 18 to 75 years (at Screening), inclusive for Cohort 1 or Cohort 2, or
 - [REDACTED]
 - [REDACTED]
2. Have had UC diagnosed at least 3 months prior to first investigational drug administration. The diagnosis should be confirmed by clinical and endoscopic evidence and corroborated by a histopathology report (note: endoscopy and histopathology may be performed at Screening if no prior report is readily available)
3. Evidence of UC extending ≥ 15 cm from the anal verge as determined by Baseline endoscopy (flexible sigmoidoscopy or colonoscopy)
4. Have active UC defined as a complete Mayo score of 6 to 12 inclusive, with endoscopic subscore of ≥ 2 , a rectal bleeding score of ≥ 1 , and a stool frequency score ≥ 1
5. Must be currently receiving treatment with at least 1 of the following therapies and must continue on these therapies during Induction:
 - Oral aminosalicylates at a therapeutic dose for their disease (eg, mesalamine, sulfasalazine, olsalazine, balsalazide), with the dose stable for at least 3 weeks prior to Screening endoscopy
 - Prednisone (doses ≤ 20 mg per day) or equivalent receiving a stable dose for at least 2 weeks prior to Screening endoscopy
 - Budesonide MMX therapy receiving a stable dose for at least 2 weeks prior to Screening endoscopy
6. Have undergone colonoscopy (or are willing to undergo colonoscopy during Screening):
 - within the past 2 years, to screen for dysplasia (unless otherwise recommended by local and national guidelines) if the patient has had left-sided colitis of > 12 years duration or total/extensive colitis of > 8 years duration
 - within the past 5 years, to screen for polyps if the patient age is > 45 years

- If oral aminosalicylates or corticosteroids have been recently discontinued, they must have been stopped for at least 2 weeks prior to the endoscopy used for Baseline Mayo score

7. Females of childbearing potential (FCBP)[¶]:

Must agree to practice a highly effective method of contraception[£] throughout the trial until completion of the 90-day Safety Follow-up Visit. Highly effective methods of contraception are those that alone or in combination result in a failure rate of a Pearl index of less than 1% per year when used consistently and correctly. Acceptable methods of birth control in the trial are the following:

- combined hormonal (oestrogen and progestogen containing) contraception, which may be oral, intravaginal, or transdermal
- progestogen-only hormonal contraception associated with inhibition of ovulation, which may be oral, injectable, or implantable
- placement of an intrauterine device (IUD)
- placement of an intrauterine hormone-releasing system (IUS)
- bilateral tubal occlusion
- vasectomized partner
- complete sexual abstinence

Periodic abstinence (calendar, symptothermal, post-ovulation methods), withdrawal (coitus interruptus), spermicides only, and lactational amenorrhoea method are not acceptable methods of contraception.

8. Must provide written informed consent/assent and have the ability to be compliant with the schedule of protocol assessments. The parent/legal guardian of the adolescent must sign an informed consent form. In addition, adolescent patients must also agree to participate in the study by signing an assent.
9. Patients must have documentation of positive Varicella zoster virus (VZV) immunoglobulin G (IgG) antibody status or complete VZV vaccination at least 30 days prior to randomization

[¶] For the purposes of this study, a female patient is considered to be of childbearing potential if she is ≥ 12 years of age or has reached menarche, whichever occurred first, and 1) has not undergone a hysterectomy (the surgical removal of the uterus) or bilateral oophorectomy (the surgical removal of both ovaries) or 2) has not been postmenopausal for at least 24 consecutive months (that is, has had menses at any time during the preceding 24 consecutive months)

[£] Contraception Education: Counselling about pregnancy precautions and the potential risks of fetal exposure must be conducted for FCBP. The Investigator will educate all FCBP about the different options of contraceptive methods or abstinence at the Screening and Baseline visits, as appropriate. The patient will be re-educated every time her contraceptive measures/methods or ability to become pregnant changes. The female patient's chosen form of contraception must be effective by the time the female patient is randomized into the study (for example, hormonal contraception should be initiated at least 28 days before baseline).

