 - Oral aminosalicylates at a therapeutic dose for their disease (eg, mesalamine, sulfasalazine, olsalazine, balsalazide), with the dose stable for at least 3 weeks prior to Screening endoscopy
 - Prednisone (doses ≤ 20 mg per day) or equivalent receiving a stable dose for at least 2 weeks prior to Screening endoscopy
 - Budesonide MMX therapy receiving a stable dose for at least 2 weeks prior to Screening endoscopy
6. Have undergone colonoscopy (or are willing to undergo colonoscopy during Screening):
 - within the past 2 years, to screen for dysplasia (unless otherwise recommended by local and national guidelines) if the patient has had left-sided colitis of > 12 years duration or total/extensive colitis of > 8 years duration
 - within the past 5 years, to screen for polyps if the patient age is > 45 years
 - If oral aminosalicylates or corticosteroids have been recently discontinued, they must have been stopped for at least 2 weeks prior to the endoscopy used for Baseline Mayo score
7. Females of childbearing potential (FCBP):

Must agree to practice a highly effective method of contraception throughout the trial until completion of the 90-day Safety Follow-up Visit. Highly effective methods of contraception are those that alone or in combination result in a failure rate of a Pearl index of less than 1% per year when used consistently and correctly. Acceptable methods of birth control in the trial are the following:

 - combined hormonal (oestrogen and progestogen containing) contraception, which may be oral, intravaginal, or transdermal
 - progestogen-only hormonal contraception associated with inhibition of ovulation, which may be oral, injectable, or implantable
 - placement of an intrauterine device (IUD)
 - placement of an intrauterine hormone-releasing system (IUS)
 - bilateral tubal occlusion
 - vasectomized partner
 - complete sexual abstinence

Periodic abstinence (calendar, symptothermal, post-ovulation methods), withdrawal (coitus interruptus), spermicides only, and lactational amenorrhoea method are not acceptable methods of contraception.

8. Must provide written informed consent/assent and have the ability to be compliant with the schedule of protocol assessments. The parent/legal guardian of the adolescent must sign an informed consent form. In addition, adolescent patients must also agree to participate in the study by signing an assent.

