Note: Adult patients in Cohort 1 will be randomized to receive RPC1063 or placebo in a 2:1 ratio in a double-blinded manner. Adult patients in Cohort 2 will receive RPC1063 in an open-label manner. Adult patients in clinical response at Week 10 of the IP who were randomized to placebo (Cohort 1) will continue to receive placebo in the MP in a double-blind manner. Only responders assigned to RPC1063 (Cohort 1 and 2) in the IP will be randomized to receive RPC1063 or placebo in a 1:1 ratio in a double-blinded manner when entering the MP.

[figure not shown]

Table 1: Schedule of Events

Trial Procedures	Screening	Induction			Maintenance							Early Term ^g	Safety Follow-up ^h	
		Dose Escalation	Assigned Dose		Treatment									
(Visit Label)	Day -35 to 0	Visit I 1 ^{a,b} (Week 0)	Visit I 2 ^a (Week 5)	(EoT) Visit I 3 ^b (Week 10)	Visit M 1 ^{b,c} (Week 0)	Visit M 2 (Week 8)	Visit M 3 (Week 18)	Visit M 4 (Week 30)	Relapse Visit (When Indicated)	(EoT) Visit M 5 ^b (Week 42)	Day 294±10	Day of Early Term	Last dose + 30 to 60 days	Last dose + 90 days ± 10 days ⁱ
(Overall Duration)	Day -35 to 0	0 weeks	5 weeks	10 weeks	10 weeks	18 weeks	28 weeks	40 weeks		52 weeks				
Informed consent/assent	X													
Inclusion/exclusion criteria	X	X			X									
Demographics	X													
Medical history ^{d,e}	X	X												
Viral serology ^f	X													
Stool culture ^g	X													
Randomization		X			X									
Dispense investigational drug		X	X	X ^b	X	X	X	X	X	X				
Administer investigational drug at clinic		X		X	X						X			
Review drug compliance			X	X	X	X	X	X	X	X	X	X		
Prior and concomitant medications	X	X	X	X	X	X	X	X	X	X	X	X	X	X
Medical procedures (non-trial)		X	X	X	X	X	X	X		X	X	X		

	Trial Procedures	Screening	Induction			Maintenance						Early Term ⁹	Safety Follow-up ⁸		
			Dose Escalation	Assigned Dose		Treatment									
(Visit Label)	(Visit Day and Window)	Day -35 to 0	Visit I 1 ^{a,b} (Week 0)	Visit I 2 ^w (Week 5)	(EoT) Visit I 3 ^b (Week 10)	Visit M 1 ^{b,c} (Week 0)	Visit M 2 (Week 8)	Visit M 3 (Week 18)	Visit M 4 (Week 30)	Relapse Visit (When Indicated)	(EoT) Visit M 5 ^b (Week 42)	Day of Early Term	Last dose + 30 to 60 days	Last dose + 90 days ± 10 days ^t	
(Overall Duration)			0 weeks	5 weeks	10 weeks	10 weeks	18 weeks	28 weeks	40 weeks		52 weeks				
Safety Assessments	Adverse events ^z		X	X	X	X	X	X	X	X	X	X	X	X	
	12-Lead ECG	X	X		X						X	X		X ^y	
	Vital signs	X	X	X	X	X	X	X	X		X	X	X	X ^y	
	Hematology ^v	X	X	X	X	X	X	X	X		X	X	X	X	

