- ^l At Screening, a flexible sigmoidoscopy may be used if a colonoscopy is not required. A colonoscopy will be required if the patient has had left-sided colitis of > 12 years duration or total/extensive colitis of > 8 years duration and has not had a colonoscopy within 2 years (unless otherwise recommended by local and national guidelines) of the screening date to rule out dysplasia, or if the patient's age is > 45 years and the patient has not had a colonoscopy within 5 years to screen for polyps. The screening endoscopy must be completed no more than 21 days prior to randomization. A flexible rectosigmoidoscopy will be performed at Week 5 or later for adolescent patients who meet clinical symptom criteria for early discontinuation, with the understanding that the procedure may occur within approximately 7 days from the last visit prior to entering the OLE, to allow for preparation. The final decision to discontinue the patient early for entry into the OLE will be left to the discretion of the Investigator based on the Partial Mayo score and the endoscopy score.
- ^m Sigmoidoscopy should be performed no more than 10 days prior to the I 3 visit date in Induction and no more than 10 days prior to the M 5 visit date in Maintenance.
- ⁿ At Screening, patients will be issued with a Mayo diary and will be trained in the completion of the diary.
- ^o The Mayo partial clinical score on Visit I 1 should be combined with the central endoscopic read in order to assess the patient for "Mayo Score" entrance criteria.
- ^p DLCO, if locally available, will be done at Screening, Visit I 3, Visit M 3, and M 5/Early Term visit.
- ^q Early Term procedures performed at the Relapse Visit do not need to be repeated for patients who are early terminating due to relapse.

- ^r In cases when a patient's End of Treatment (Week 42 of Maintenance) visit and the first visit of the open-label extension study do not occur on the same day, an extra bottle of investigational drug may be dispensed to cover the period of time prior to entering the open-label extension.
- ^s The Safety follow-up visit should occur between 30 days to 60 days and at 90 days (± 10 days) after the last dose of investigational drug in the RPC01-3101 trial. However, if the patient continues treatment in the open-label extension, the safety follow-up visits are not required for the RPC01-3101 trial.

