12.2.9. Procedures in Case of Pregnancy

If a urine pregnancy test is positive, the patient will be instructed to suspend further study dosing. If the test was performed by the patient between scheduled visits, a follow-up appointment will be scheduled as soon as possible. A serum pregnancy test will be performed to confirm the result.

Pregnancy in itself is not regarded as an AE unless there is a suspicion that an investigational product may have interfered with the effectiveness of a contraceptive medication; however, the outcome of all pregnancies (spontaneous miscarriage, elective termination, normal birth,

or congenital abnormality) must be followed up and documented even if the patient was discontinued from the trial. In cases of live birth, the infant will be followed for up to a year.

Male patients should also be instructed to notify the Investigator in the event that their female partner becomes pregnant. Attempts should be made to follow female partners of trial patients, if they should become pregnant. The Investigator must obtain informed consent/assent from the pregnant partner of a trial patient prior to collecting data on her pregnancy and its outcome.

All reports of congenital abnormalities/birth defects are SAEs. Spontaneous miscarriages should also be reported and handled as SAEs. Elective abortions without complications should not be handled as AEs. All outcomes of pregnancy must be reported to the Sponsor and/or its designee. In cases of live birth, the infant will be followed for up to a year.

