JCV infection resulting in PML has been observed in subjects treated with MS therapies and has been associated with some risk factors (eg, polytherapy with immunosuppressants, severely immunocompromised subjects). No cases of PML were identified in clinical trials with ozanimod. Should symptoms present that are suggestive of PML, investigators should hold ozanimod and perform appropriate diagnostic evaluation. If confirmed, treatment with ozanimod should be discontinued.

Posterior Reversible Encephalopathy Syndrome (PRES):

In controlled clinical trials with ozanimod, one case of PRES was reported in a subject with Guillain-Barré syndrome. A relationship of PRES to ozanimod is uncertain. It has been observed with other S1P receptor modulators. If PRES is suspected, treatment with ozanimod should be discontinued by the investigator.

Embryofetal Toxicity in Exposed Pregnant Females:

There are no adequate and well-controlled studies in pregnant women. In animals, findings at similar exposure levels included embryo- fetal death, abnormal/delayed ossification, and abnormalities of the viscera and large blood vessels. There have been no reports of teratogenicity in the ozanimod clinical trials.

The use of ozanimod is not recommended during pregnancy and in women of childbearing potential not using contraception. Women of child-bearing potential should use effective contraception during treatment and for a minimum of 90 days after stopping treatment and must stop study treatment in the event of a diagnosis of pregnancy.

Malignancy:

Nonclinical testing found no carcinogenic effect through extensive genetic toxicology testing, in vivo carcinogenicity studies, and assessment of proliferative lesions in the general toxicology studies. The overall incidence of malignancies observed for patients on ozanimod is generally comparable to rates reported in the literature and health authority medical reviews for an age-matched population. The malignancies reported do not demonstrate any particular pattern and are not typical of those observed in an immunosuppressed population.

Infections:

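### The contraception requirement can end 80 days after the last dose, although Appendix 3 of the protocol states a minimum of 90 days

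*Protocol*

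**What the plan says.** Three parts of the protocol bear on when contraception may stop.

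- **Criterion 7**, in the Synopsis and again in Section 8.1, sets the obligation. In Section 8.1 it runs "throughout the trial until completion of the 90-day Safety Follow-up Visit". The Synopsis reads: "Must agree to practice a highly effective method of contraception throughout the trial until completion of the 90-day Safety Follow-up Visit". The end point is a visit; no number of days after the last dose is given.
- **Table 1 (Section 7.1)** fixes when that visit may take place. The column header gives "Last dose + 90 days ± 10 days", and footnote s repeats the window: "at 90 days (± 10 days) after the last dose of investigational drug". The same footnote adds that "if the patient continues treatment in the open-label extension, the safety follow-up visits are not required" for this trial.
- **Appendix 3**, under embryofetal toxicity, says that women of childbearing potential "should use effective contraception during treatment and for a minimum of 90 days after stopping treatment".

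Section 12.2.9 deals with pregnancies that do occur: their outcome "must be followed up and documented even if the patient was discontinued from the trial".

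**The concern.** Criterion 7 ends at a visit with a symmetric window, while Appendix 3 states a minimum, which allows nothing on the short side. A site that follows criterion 7 and Table 1 exactly can therefore complete a woman's obligation before the period the protocol itself gives as the least acceptable.

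The risk behind the rule is serious. Appendix 3 reports embryofetal death and malformations in animals at similar exposure levels and says there are no adequate studies in pregnant women. It also says that no teratogenicity has been reported in the clinical trials. What is at stake is a few days of protection for some women after they stop treatment. No endpoint, analysis or error rate is involved.

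**Working it through.** **Inputs**

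- Target day of the visit: *T* = 90 days after the last dose (Table 1 header and footnote s).
- Tolerance: *w* = 10 days (same places).
- Minimum contraception after stopping treatment: *M* = 90 days (Appendix 3). This is a stated figure with no calculation behind it to reproduce.
- Assumption: the day of the last dose and the day treatment stops are the same.

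**Visit window**

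- Earliest permitted day: *T* − *w* = 90 − 10 = 80.
- Latest permitted day: *T* + *w* = 90 + 10 = 100.
- Number of permitted days: 100 − 80 + 1 = 21.

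**Shortfall against the minimum**

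- Permitted days before day 90: days 80 to 89, that is 89 − 80 + 1 = 10 of 21.
- For a visit on day *d* < 90 the shortfall is *M* − *d*. At *d* = 89 it is 90 − 89 = 1 day; at *d* = 80 it is 90 − 80 = 10 days.
- For *d* ≥ 90 there is no shortfall.

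**Does other text close the gap?** These are the places where a 90-day floor could have been written.

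| Place | What it covers | Extends contraception to day 90? |
|---|---|---|
| Section 8.1, contraception education note | Counselling, choice of method, method effective by randomization | No |
| Section 12.1.11 and Table 1 footnote i | Home pregnancy tests until the same visit; serum confirmation afterwards if needed | No |
| Section 12.2.5 | Serious adverse events within 90 days of the last dose | No; reporting only |
| Section 12.2.9 | Follow-up of pregnancy outcomes | No; acts after conception |

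Elsewhere the protocol does count days rather than rely on the visit. Section 12.2.5 adds a 90-day limit to the last visit for serious adverse events. Section 9.5.2 records concomitant therapy until 90 days after the final dose. Criterion 7 has no such limit.

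**With a floor added.** If the obligation ran to the later of day 90 and the visit, its earliest end would be max(90, 80) = day 90 and the largest shortfall 90 − 90 = 0 days.

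**The case against.** The strongest reply is that the two texts can both be obeyed. Criterion 7 is an entry condition and tells nobody to stop contraception at the visit; Appendix 3 belongs to the same protocol and still applies. On this view only a cross-reference is missing. The texts also differ in kind: Appendix 3 is a benefit-risk narrative that recommends effective contraception, whereas criterion 7 demands a highly effective method.

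Part of this stands. A woman who follows both texts is protected, and criterion 7 is the stricter one on method. But it defines when the commitment she makes is complete, and that can be before day 90. A stricter method does not supply the missing days.

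Two further points limit the practical effect:

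- **Counselling.** As far as the flattened Table 1 can be read, contraception education continues to the follow-up visit 30 to 60 days after the last dose. This makes an early stop less likely but sets no end date.
- **Few women are exposed.** Induction non-responders, maintenance completers and patients who relapse may enter the extension (SAP Section 4.1). That leaves women who stop treatment, do not enter it, are seen before day 90, and then stop contraception before day 90.

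There is also a fair objection to the remedy. Appendix 3 records that 645 adults had already entered Cohort 1 and 367 Cohort 2, and changing an inclusion criterion does not by itself bind people already enrolled. This affects how the change is delivered, not whether the texts differ.

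**Conclusion.** The concern holds. Criterion 7 can be satisfied in full 1 to 10 days before the minimum in Appendix 3, whenever the follow-up visit falls on days 80 to 89 after the last dose. No visible text makes up the difference.

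The point is minor. The gap is at most 10 days, the number of women affected cannot be derived from the documents, and the figure of 10 days in 21 describes the window, not how often visits occur early. It concerns contraception only: the protocol states no 90-day minimum for pregnancy testing. The conclusion rests on the visible protocol text. The consent pages are not available, and if they already state a 90-day minimum, the gap is confined to the protocol's wording.

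**What to change.** In criterion 7, in both the Synopsis and Section 8.1, end the requirement at *the later of 90 days after the last dose and completion of the 90-day Safety Follow-up Visit*. Make the same change in the consent text if it uses the present wording. To reach women already enrolled, tell sites to advise contraception until at least day 90 when the visit is early. The sponsor may also wish to align the end of home pregnancy testing, but nothing in the protocol requires it.

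The drafting cost is one phrase in two places, plus the consent text if it matches. If issued as an amendment, it goes through ethics committee review, with re-consent where the committee directs it (Sections 16.1 and 16.3), across approximately 325 sites; it could be held for the next planned amendment with the site instruction sent at once. For patients, the cost is 1 to 10 more days of contraception for those seen on days 80 to 89 and nothing for the rest. No visit or test is added.

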8.2. Patient Exclusion Criteria

Patients will not be entered in the trial for any of the following reasons:

Exclusions Related to General Health:

1. Have severe extensive colitis as evidenced by:
 - Physician judgment that the patient is likely to require colectomy or ileostomy within 12 weeks of Baseline
 - Current or recent (within 3 months) evidence of fulminant colitis, toxic megacolon, or bowel perforation
2. Diagnosis of Crohn's disease or indeterminate colitis or the presence or history of a fistula consistent with Crohn's disease or microscopic colitis or radiation colitis or ischemic colitis
3. Have positive stool examination for pathogens (ova and parasites, bacteria) or positive test for toxin producing *Clostridium difficile* (*C. difficile*) at Screening. PCR (polymerase chain reaction) examination of the stool for *C. difficile* may be used to exclude false positives. If positive, patients may be treated and retested. Documentation of a negative test result for pathogens (ova and parasites, bacteria) is required within 60 days of Day 1.
4. Pregnancy, lactation, or a positive serum beta-human chorionic gonadotropin (β -hCG) measured during Screening
5. Clinically relevant hepatic, neurological, pulmonary, ophthalmological, endocrine, psychiatric, or other major systemic disease making implementation of the protocol or interpretation of the trial difficult or that would put the patient at risk by participating in the trial
6. Clinically relevant cardiovascular conditions, including history or presence of:
 - Recent (within the last 6 months) occurrence of myocardial infarction, unstable angina, stroke, transient ischemic attack, decompensated heart failure requiring hospitalization, Class III/IV heart failure, sick sinus syndrome, or severe untreated sleep apnea
 - For Adult patients: Prolonged Fridericia's corrected QT interval (QTcF; QTcF > 450 msec for males, > 470 msec for females), or at additional risk for QT interval prolongation (eg, hypokalemia, hypomagnesemia, congenital long-QT syndrome)
 - [REDACTED]
 - Resting HR < 55 bpm when taking vital signs as part of a physical exam at Screening

7. History of diabetes mellitus type 1, or uncontrolled diabetes mellitus type 2 with glycosylated Hb (HbA1c) > 9%, or diabetic patients with significant comorbid conditions such as retinopathy or nephropathy
8. History of uveitis (within the last year) or macular edema
9. Subject has a known active bacterial, viral, or fungal infection [excluding fungal infection of nail beds, minor upper respiratory tract infections, and minor skin infections], a mycobacterial infection (including tuberculosis [TB] or atypical mycobacterial disease), or any major episode of infection that required hospitalization or treatment with intravenous (IV) antibiotics within 30 days of Screening or oral antibiotics within 14 days of Screening
10. Recurrent or chronic infection (eg, hepatitis A, B, or C, human immunodeficiency virus [HIV]); recurrent urinary tract infections are allowed.
11. History of cancer, including solid tumors and hematological malignancies (except basal cell and in situ squamous cell carcinomas of the skin or uterine cervix that have been excised and resolved) or colonic mucosal dysplasia
12. History of alcohol or drug abuse within 1 year prior to randomization
13. History of or currently active primary or secondary immunodeficiency

Exclusions Related to Medications:

14. History of treatment with a biologic agent within 8 weeks or 5 elimination half-lives (whichever is less) of that agent prior to randomization
15. History of treatment with an investigational agent within 5 elimination half-lives of that agent prior to randomization
16. History of treatment with topical rectal 5-aminosalicylic acid or topical rectal steroids within 2 weeks of Screening endoscopy or anti-motility medications (such as diphenoxylate/atropine) during Screening
17. Receipt of a live vaccine or live attenuated vaccine within 4 weeks prior to randomization
18. Previous treatment with lymphocyte-depleting therapies (eg, Campath, anti-CD4, cladribine, rituximab, ocrelizumab, cyclophosphamide, mitoxantrone, total body irradiation, bone marrow transplantation, alemtuzumab, daclizumab)
19. Have had treatment with cyclosporine, tacrolimus, sirolimus, or mycophenolate mofetil (MMF) within 16 weeks of Screening or tofacitinib within 2 weeks of Screening
20. Previous treatment with D-penicillamine, leflunomide, or thalidomide
21. Previous treatment with natalizumab, fingolimod or etrasimod
22. History of treatment with intravenous immunoglobulin (IVIg) or plasmapheresis within 3 months prior to randomization

23. Planned concurrent treatment with immunosuppressive agents (eg, azathioprine [AZA], 6-mercaptopurine [6-MP], or methotrexate) after randomization. Patients receiving AZA, 6-MP, or methotrexate at Screening must discontinue treatment with these agents prior to randomization
24. Chronic non-steroidal anti-inflammatory drug (NSAID) use (note: occasional use of NSAIDs and acetaminophen [eg, headache, arthritis, myalgias, or menstrual cramps] and aspirin up to 325 mg/day is permitted)
25. Treatment with Class Ia or Class III anti-arrhythmic drugs or treatment with two or more agents in combination known to prolong PR interval
26. Apheresis (eg, Adacolumn apheresis) within 2 weeks of randomization
27. Patients who were primary non-responders to 2 or more biologic agents, approved for the treatment of UC (eg, anti-TNF agents or vedolizumab)
28. Patient receiving treatment with breast cancer resistance protein (BCRP) inhibitors (eg, cyclosporine, eltrombopag)
29. Is receiving treatment with any of the following drugs or interventions within the corresponding timeframe:
 - At randomization
 - CYP2C8 inhibitors (eg, gemfibrozil or clopidogrel) and inducers (eg, rifampicin)
 - Two weeks prior to randomization
 - Monoamine oxidase inhibitors (eg, selegiline, phenelzine)

Exclusions Related to Laboratory Results:

31. Serum creatinine > 1.4 mg/dL for females or > 1.6 mg/dL for males
32. Liver function impairment or persisting elevations of aspartate aminotransferase (AST) or alanine aminotransferase (ALT) > 2 times the upper limit of normal (ULN), or direct bilirubin > 1.5 times the ULN
33. Platelet count < 100,000/ μ L
34. Hemoglobin < 8.0 g/dL
35. Neutrophils < 1500 / μ L
36. Absolute white blood cell count < 3500/ μ L
37. Absolute lymphocyte count < 800/ μ L
38. ECG showing any clinically significant abnormality
39. Forced expiratory volume at 1 second (FEV₁) or forced vital capacity (FVC) < 70% of predicted values at Screening

